#### 9.1.1 Demographic and baseline characteristics

Demographic characteristics (age, sex, educational level), lens status, anti-glaucoma medication, and other previous and concurrent treatments will be tabulated for the safety set.

#### 9.1.2 Subject Disposition

The number and percentage of those who complete the follow-up will be tabulated for the safety set. The number and percentage of early withdrawals will also be tabulated, along with the reason for the screen failure or drop-out.

#### 9.1.3 Safety Analysis

The incidence and nature of adverse events observed within the safety population will be analyzed by descriptive and explorative statistical methods.

Safety will be described in detail by frequency, seriousness, severity, nature and duration of events.

Number of adverse events as well as the number and relative frequency of patients reporting adverse events will be tabulated by system organ class and preferred terms. The same table will be prepared for serious adverse events. In addition, the number and relative frequency of patients reporting adverse events will be tabulated by system organ class and preferred terms in dependence on the worst severity and worst causal relationship. Furthermore, number of adverse device effects as well as the number and frequency of patients reporting adverse device effects will be tabulated by system organ class and preferred terms and not by event description as stated in the protocol.

 Implantata Ophthalmic Products GmbH	Clinical Investigation Plan ARGOS-SC01_Follow-up	Revision C  Page 70 of 97
--	---	---------------------------------

#### **9.1.4 Performance Analysis**

The probability distribution of the difference of the paired measurements grouped within 1 mmHg will be compared to the primary objective of the accepted 65% of the measurements to agree between +/- 5 mmHg for > 60 measurement pairs.

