Data Analysis and Statistics	
Primary Endpoint
 
Performance
 
 
- Level of Agreement between measurements made using GAT, Pascal DCT and the ARGOS-SC system from V09 (month 12) through V13 (month 36).
 
 
Secondary Endpoints
 
Safety
 
 
- Number of patients experiencing a device-related SAE (SADE) from V09 (month 12) to V13 (month 36)
 
- Incidence, nature, severity and seriousness of observed adverse events and adverse device events at any time from month 12 (V09) through month 36 (V13).
 
 
Performance
 
 
- Repeatability of the ARGOS-SC measurement
 
- Incidence, nature and seriousness of observed device malfunctions from month 12 (V09) throughout month 36 (V13) months follow-up period.
 
 
Utility
 
 
- User acceptance of the ARGOS-SC system at the investigational site by means of evaluation of physician acceptance questionnaires (by investigators)
 
- User acceptance of the ARGOS-SC system at home by means of evaluation of patient acceptance questionnaires (patients)
 
- Daily IOP self-measurement profiles (patients)
 

 Implantata Ophthalmic Products GmbH	Clinical Investigation Plan ARGOS-SC01_Follow-up	Revision C  Page 9 of 97
--	---	--------------------------------

	
Statistical analysis
 
Safety analysis
 
AEs, SAEs, ADEs and SADEs will be listed and analyzed by descriptive and explorative statistical methods.
 
Performance analysis
 
The probability distribution of the difference of the paired measurements grouped within 1 mmHg will be compared to the primary objective of the accepted 65% of the measurements to agree between +/- 5 mmHg for > 60 measurements pairs.
 
Follow-up Analysis
 
A safety and performance summary will be provided after V10, V11, V12 and V13 when all included patients have undergone the appropriate visit.

Data Collection	Data will be collected using a Case Report Form (CRF).
Study Duration	The overall study duration for each individual subject is up to 24 months.

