#### **9.8 Treatment of missing, unused and spurious data, including drop-outs and withdrawals**

All data of the patients will be used as available. All analyses will be performed on observed cases only. Missing data will not be replaced. Implausible values will be only excluded from the analysis if reasonable. The reason for exclusion will be given in the footer of the table or description of the figure. Patients terminating the trial prematurely due to whatever reason will be evaluated like any patient completing the trial as per protocol, within the analysis sets they qualify for.

Subjects who dropped out during a scheduled visit will be counted for that visit.

 Implantdata Ophthalmic Products GmbH	Clinical Investigation Plan ARGOS-SC01_Follow-up	Revision C  Page 72 of 97
---	---	---------------------------------

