7.2 Handling of missing data

In general, missing data will not be replaced. In tables of categorical data, missing data will be included as 'Missing' and included in the calculation of percentages.

If not otherwise specified and the calculation of periods requires the full date format dd-mm-yyyy, missing start date entries will be set to the first possible day of the month for a missing day and in case of a missing month, the first possible month of a year will be set. Missing stop date entries will be set to the last possible day of the month for a missing day and in case of a missing month, the last possible month of a year will be set.

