8.1.2 Statistical outputs

8.1.2.1 Tables and graphics

Percentages will be based on the number of subjects in the analysis set.

Categorical variables will be summarized by the number of patients (n) and percentages (%). Percentages will be rounded to one decimal place.

In addition, for the primary endpoints (response rates) the 95% confidence intervals will be calculated.

Continuous variables will be summarized using descriptive statistics, including

- number of patients with non-missing data (n)
- arithmetic mean (Mean)
- 95% confidence interval of mean (if indicated)
- standard deviation (SD)
- median (Median)
- lower (25%, Q1) and upper (75%, Q3) quartile
- minimum (Min) and maximum (Max).

Analyses by visit will be performed irrespective of any time window deviations.

Some mock-up tables are presented in the appendix of this SAP.

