8.5 Primary endpoint

8.5.1 Performance

Level of agreement between measurements made using GAT, Pascal DCT and ARGOS-SC system at visit V09 - V13.

The primary outcome measures of the study eye are:

- Average of 2 – 3 measurements using GAT system at visit V09 – V13
- Average of 2 – 3 measurements using ARGOS-SC system at visit V09 – V13 roughly contemporaneous with the GAT measurements

Descriptive statistics for the GAT and ARGOS-SC measures per visit.

Descriptive statistics for the absolute difference between ARGOS-SC and GAT measures per visit.

The absolute difference between the ARGOS-SC and GAT measures will be scaled in $\leq 5\text{mmHg}$ and $> 5\text{ mmHg}$ and the frequency distribution will be displayed.

The concordance of the intraindividual measurement values of GAT and ARGOS-SC will be indicated by the concordance correlation coefficient r_{ccc} (→ see section 11.1), separate for each visit.

The Bland-Altman (mean-difference) plot and a X-Y -plot (Scatter-Plot) should illustrate the comparison of the two methods (→ see section 11.2).

The level of agreement between Pascal DCT and ARGOS-SC will be evaluated analogously.

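### The SAP's agreement output is by visit only (at most 24 averaged pairs each) and omits the protocol's comparison with 65% of more than 60 pairs within ±5 mmHg, without declaring the change

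*Protocol*

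**What the plan says.** **Protocol.** The synopsis and section 9.1.4 describe the same analysis: "The probability distribution of the difference of the paired measurements grouped within 1 mmHg will be compared to the primary objective", that objective being the "accepted 65% of the measurements to agree between +/- 5 mmHg for > 60 measurement pairs". Footnotes 1 (synopsis) and 4 (to 9.1.4) say the objective is to be adjusted if that number of pairs is not reached; neither gives a rule. The protocol does not define a pair. Section 9.2 sets a maximum of 24 patients and leaves the minimum to the sponsor. On missing data, section 9.8 states: "All analyses will be performed on observed cases only".

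**SAP.** The introduction names Protocol Rev. C as its basis, and section 4.2.1 keeps the V09-V13 window. Section 8.5.1 averages the readings of each method, which gives one pair per patient and visit. It then plans "Descriptive statistics for the absolute difference between ARGOS-SC and GAT measures per visit", a split of the absolute difference at 5 mmHg, and a concordance coefficient "separate for each visit". DCT is handled in the same way. Each of Figures 1-20 covers one visit, and the Table 2.1.1 shell has columns V09 to V13 only.

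On percentages, section 7.2 says of categorical tables that "missing data will be included as 'Missing' and included in the calculation of percentages", and section 8.1.2.1 adds: "Percentages will be based on the number of subjects in the analysis set". The same section says that "for the primary endpoints (response rates) the 95% confidence intervals will be calculated", with no method named. Section 8.1.3 rules out statistical tests. Section 9 lists two changes from the protocol: self-measurements not recorded and interim analyses not performed.

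**The concern.** The protocol gives its primary objective one concrete yardstick, and the SAP does not apply it. The omission does not look like a general choice against pooling, because SAP 8.6.2 asks for per-visit and overall results for the secondary repeatability standard deviations.

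If the SAP stays as it is, anyone who writes the report and wants to answer the protocol's question must decide, with the data in view, whether to pool the visits, which denominator to use, which interval to give and, at 60 or fewer pairs, what becomes of the 65%. Each is easy to settle now. Settled later, each lets the headline agreement figure be questioned.

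**Working it through.** **Inputs.** Maximum 24 patients (Protocol 8.3.6, 9.2); five visits, V09-V13; one averaged pair per patient, visit and comparator (SAP 8.5.1); benchmark 65% within ±5 mmHg for more than 60 pairs (Protocol 9.1.4). No derivation of 65% or of 60 is given, so there is no calculation to reproduce.

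**1. Pair counts per comparator.**
- One visit: at most 24.
- V09-V13 combined: 24 × 5 = 120.
- Twelve fully followed patients: 12 × 5 = 60, which is not more than 60, so the footnote applies. Thirteen: 13 × 5 = 65.

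With the SAP's averaged pair, the condition can be met only by combining visits. Sixty or fewer pairs is a real possibility: 24 is a ceiling, the minimum is open, and DCT is measured only where available.

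**2. What one visit can show.** With 24 pairs, the exact (Clopper-Pearson) 95% interval contains 65% for every count from 11 (45.8%) to 20 (83.3%). At 16/24 = 66.7% it runs from 44.7% to 84.4%. A single visit says little about 65%.

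**3. Denominator.** The wording of Protocol 9.8 (observed cases) conflicts with SAP 7.2 and 8.1.2.1 (missing counted, analysis set). But the Table 2.1.1 shell heads the ≤5/>5 split with n, which the SAP abbreviations define as patients with non-missing data, and has no row for missing. The shell therefore looks like observed cases, and the SAP is unclear within itself. Illustration, assuming 20 of 24 observed at a visit:
- 15/20 = 75.0%; 15/24 = 62.5%. The two figures fall on opposite sides of 65%.
- 65% of 24 is 15.6, so 16 agreeing pairs are needed, and 16/20 = 80%.

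**4. Interval for a pooled figure.** This informs the design of the remedy, since the SAP plans no pooled interval. Each patient contributes up to five pairs. The documents give no intraclass correlation (ICC), so 0.3, 0.5 and 0.7 are assumed. At 90/120 = 75%:
- Independent pairs: 0.75 ± 1.96 × √(0.1875/120) = 67.3% to 82.7%, width 15.5 points.
- Design effect 1 + 4 × ICC = 2.2, 3.0, 3.8; effective n = 120/design effect = 54.5, 40.0, 31.6. On the logit scale with t(23) = 2.069: 61.1-85.1%, 58.5-86.5%, 56.2-87.5%, or about 24, 28 and 31 points wide.
- Thirteen patients with all five visits, simulated at a true rate of 75%: median widths about 35, 41 and 47 points for the corrected interval.

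Simulated coverage of a nominal 95% interval (beta-binomial, five visits, true rate 75%, ICC 0.3/0.5/0.7):

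| Interval | 24 patients | 13 patients |
|---|---|---|
| Pairs treated as independent (Wald) | 82/74/69% | 78/71/65% |
| Robust variance, uncorrected | 92% | 89-90% |
| Bias-corrected robust variance, logit scale, t | 96-97% | 97% |

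**The case against.** **The pair is undefined in the protocol, so the cap of 24 is not the protocol's.** This stands. Pairing individual sensor readings would give 24 × 3 = 72 at one visit. A reader might infer that no visit could ever exceed 60 pairs; that is true only of the SAP's averaged pair. The SAP, however, has chosen that pair, and under it the by-visit output cannot meet the condition.

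**The denominator conflict is thin.** Partly right. SAP 7.2 and 8.1.2.1 are general conventions, and the Table 2.1.1 shell is laid out for observed cases. A reader might infer that the SAP will count missing pairs as failures in the primary result. The documents do not establish that, and no passage uses 120 possible pairs as a denominator. What remains is a conflict of wording that should be resolved.

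**Poor coverage belongs to an analysis nobody planned.** Correct. By visit there is one pair per patient and no clustering. The coverage figures show how a pooled interval should be built; they do not measure a fault in the present SAP.

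**The pooled count follows by addition.** True if the shell is followed: the five visit counts can be summed. But the sentence on the ≤5/>5 split in SAP 8.5.1 names no level, the shells are labelled as examples, and a sum made afterwards has no prespecified denominator, interval or reference value.

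**The study is exploratory.** Agreed. Protocol 9.2 and SAP 8.1.3 make everything descriptive. That limits the consequence, but a descriptive plan should still produce the description its protocol sets.

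**Conclusion.** The point holds and should be fixed before lock. The SAP does not deliver the comparison that its own protocol revision sets for the primary objective: the 65% reference, the 1-mmHg distribution and any pooled V09-V13 agreement result are absent, and section 9 does not declare this. By-visit results rest on at most 24 averaged pairs, against a condition of more than 60; pooling would give up to 120. The denominator wording is unsettled, with a possible swing from 75.0% to 62.5% if 20 of 24 pairs are observed; that missing rate is an assumption.

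A reader might go further and infer that the primary conclusion would be wrong or that a test would fail. The documents do not support this: no test is planned, the data needed are being collected, and the by-visit output is sound as far as it goes. The pair counts follow from the documents; the interval widths rest on the assumed ICCs.

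**What to change.** In the SAP, before database lock:

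1. Keep the by-visit output, which is also where sensor drift would show. Add an overall V09-V13 column to Tables 2.1.1 and 2.1.2 with the number and percentage of averaged pairs within ±5 mmHg, GAT and DCT separately, shown beside 65%.
2. Use observed pairs as the denominator for this split, show the number missing, and state this as an exception to SAP 7.2 and 8.1.2.1.
3. Give the overall percentage a descriptive 95% interval that allows for up to five pairs per patient, with a small-sample correction. One choice is a Mancl-DeRouen robust variance on the logit scale with t on patients minus one degrees of freedom. If every pair agrees, use an exact interval with the number of patients as n. No test or pass rule is added.
4. Add the 1-mmHg distribution of the signed differences for each comparator.
5. Always report the number of pairs and show the unadjusted 65% as a reference. For 60 or fewer pairs, either write the footnotes' adjustment rule into the SAP before lock, or remove footnotes 1 and 4 by approved amendment. The SAP should not simply override them, because Protocol 11.4 requires ethics committee and regulatory approval before such an amendment is implemented.

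**Cost.** SAP wording, one column in two tables and one extra display per comparator; no new data. Removing the footnotes would need a formal amendment. The interval will be wider than with naive pooling: about 24-31 points with 24 fully followed patients at 75%, and about 35-47 with 13, under ICCs of 0.3-0.7, against 15.5 for 120 pairs treated as independent. That extra width reflects the repeated pairs within patients.

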#### **9.2 Sample Size Calculation**

Given by the exploratory nature of this study, the sample size is not driven by the need for a formal statistical hypothesis test with a certain degree of power. Instead, this study is driven by the desire to obtain a clinically meaningful amount of data to evaluate the long-term safety and performance of the ARGOS-SC system in patients who have been already implanted with the study device. Therefore the maximum sample size is 24. The minimal sample size for this study is at the Sponsor's direction. This is considered to be appropriate since no experimental treatments are planned and all assessments with exception of IOP measurement using the ARGOS-SC device are established standard methods.

#### **9.3 Level of significance and the power of the clinical investigation**

Significance level is set to 0.10, Power to 80%.

#### **9.4 Interim analysis**

A safety and performance summary will be provided after V10, V11, V12 and V13 when all included patients have undergone the appropriate visit.

#### **9.5 Criteria for termination of the clinical investigation**

The participation of an individual site in the study will be discontinued if the sponsor, the investigator or the responsible ethics committee deems it necessary for any reason.

The complete study will be discontinued:

- If the sponsor and/or any responsible regulatory authority or ethic committee judges it necessary for any reason. See also Section 8.3.2 Discontinuation or Withdrawal Criteria Early Patient Withdrawal and Section 11.11 Criteria for Suspension and Premature Termination of Study

---

 In the unprobeable case this number of measurement pairs is not reached, the primary objective is to be adjusted according to the actual number of measurement pairs.

 IOP Implantata Ophthalmic Products GmbH	Clinical Investigation Plan ARGOS-SC01_Follow-up	Revision C  Page 71 of 97
---	---	---------------------------------

- If, throughout the course of the study, the DSMB comes to the conclusion that the ARGOS-SC pressure sensor would expose the subject study patients to undue risk

All patients will continue to be followed up. If the study is discontinued for safety reasons it will be proven whether explantation of all ARGOS-SC sensors deems necessary or follow-up of patients is sufficient.

#### **9.6 Procedures for reporting of deviations from the original statistical plan**

Significant deviations from the original statistical analysis plan will be listed and clarified in the final clinical investigation report.

#### **9.7 Specification of Subgroups for Analysis**

In order to permit investigation of their impact on performance and safety, information will be collected prospectively on the following variables:

- Gender
- Post-surgical complications
- Successful implantation
- Age groups
- Country of investigational site
- Educational level
- Medical History (primary underlying ophthalmic illness or injury necessitating the non-penetrating glaucoma surgery)
- Pre-treatment
- Concomitant medications

Which subgroup analyses are actually performed will be decided at a final data review meeting preceding the statistical analysis, based on the actual distribution of subjects in the study population.

#### **9.8 Treatment of missing, unused and spurious data, including drop-outs and withdrawals**

All data of the patients will be used as available. All analyses will be performed on observed cases only. Missing data will not be replaced. Implausible values will be only excluded from the analysis if reasonable. The reason for exclusion will be given in the footer of the table or description of the figure. Patients terminating the trial prematurely due to whatever reason will be evaluated like any patient completing the trial as per protocol, within the analysis sets they qualify for.

Subjects who dropped out during a scheduled visit will be counted for that visit.

 Implantdata Ophthalmic Products GmbH	Clinical Investigation Plan ARGOS-SC01_Follow-up	Revision C  Page 72 of 97
---	---	---------------------------------

## 9.9 Datasets to be analyzed

All subjects enrolled in this study will be included in the analysis since all subjects already have the ARGOS-SC sensor implanted and evaluable data for the primary performance are already recorded.

## 9.10 Site Monitoring

The study will be monitored in compliance with the Declaration of Helsinki, ISO 14155:2011, the Clinical Investigation Plan (CIP) and all applicable national and local regulations. All monitoring activities will be conducted by trained and qualified monitors, who will document each individual monitoring visit. In general, during monitoring visits the monitor will ensure that the study is being conducted according to the CIP, ISO 14155:2011, ICH GCP (International Conference on Harmonisation Good Clinical Practice) and other applicable regulations, and will compare the CRF entries to original source data. He/she will also make sure the informed consent procedure has been appropriately carried out and will ensure that all SAEs have been reported within applicable timeframes. He/she will also ensure that investigational device accountability has been maintained and will, after completion of the study, perform final accountability and arrange return or destruction of investigational products. For each patient lost to follow-up, the monitor will verify if the study center's attempted contacts with the patient, followed by contacts with the patient's family doctor, were adequate.

Detailed monitoring procedures will be described in a separate monitoring plan.

## 9.11 Data collection

Data will be collected through a Case Report Form (CRF) provided by the sponsor or its designee to the centers prior to study start. Designated site staff will enter study data in the CRF during or as soon as possible after the visit.

## 9.12 Database Management and Quality Control

The investigator is responsible for maintaining accurate, complete, and up-to-date records for each subject. This includes maintaining any source documentation related to the study. The privacy of participating subjects must be maintained. The sites will maintain a list of the subjects' names and the Patient ID assigned to each individual subject. Subjects will not be identified except by Patient ID on any document submitted to the sponsor. All documents that could identify the subject beyond the Patient ID (e.g. the signed informed consent document) must be maintained in strict confidence by the investigator, except to the extent necessary to allow inspections by the regulatory authorities and audits by the study monitor or sponsor representatives.

 Implantata Ophthalmic Products GmbH	Clinical Investigation Plan ARGOS-SC01_Follow-up	Revision C  Page 73 of 97
--	---	---------------------------------

The investigator must review the completed CRFs for each subject promptly and must confirm the accuracy of all data entered with his/her signature at the end of each documented subject's visit in the CRF. Any corrections made to data entries will be GCP conform.

During data review, data management will generate queries for any missing, out of range or questionable data and send those to the investigator for resolution. The physician will answer the query and this answer will be documented. All queries must be answered and the database locked before any (interim) analysis of the data may begin.

